4. AMENDMENTS AND UPDATES

Substantial protocol amendments/updates so far: None

Hemlibra—F. Hoffmann-La Roche Ltd Protocol BO44691, Version 2.0

5. MILESTONES

The final study report will be submitted as a standalone procedure in the EU PAS registry. The interim reports will be included in the Periodic Safety Update Report (PSUR) / Periodic Benefit Risk Evaluation Report (PBRER).

Milestone	Planned Date
Registration of protocol in the EU PAS register	Q1 2024
First Data Extraction	Q2 2025
Second Data Extraction	Q2 2027
Last Data Extraction	Q4 2030
First interim report	Q4 2025
Second interim report	Q4 2027
Final report of study results (CSR)	Q2 2031
Registration of the results in the EU PAS register	Q3 2031

6. RATIONALE AND BACKGROUND

6.1. BACKGROUND

Haemophilia A (HA) is an X-linked recessive bleeding disorder that occurs in approximately 1 in 5000 live male births. Patients with congenital HA have a deficiency or absence of blood coagulation factor VIII (FVIII), an essential component of the intrinsic pathway in the coagulation cascade (Franchini and Mannucci, 2013; Mannucci and Tuddenham, 2001). Three severity levels of the disease are distinguished based on the percentage of the normal FVIII plasma procoagulant levels, mild (>5% - <40%), moderate (1% - 5%), and severe (<1%) (White et al., 2001).

The absence or functional deficiency of FVIII leads to a lifelong bleeding tendency. Common clinical signs of congenital HA include easy bruising; prolonged bleeding after trauma or surgery; spontaneous bleeding into joints, muscles, or soft tissues; and intracranial haemorrhage, leading to frequent bleeding events with the sequelae of musculoskeletal complications, such as arthropathy, local functional deficits, haemorrhagic shock, neurocognitive defects, or even death (Stonebraker et al., 2020). These disease-related issues can have a significant impact on the health-related quality of life (HRQoL) of both adult and adolescent patients (Brown et al., 2009).

Prophylactic FVIII replacement therapy (i.e., administered on a scheduled basis with the intent to prevent bleeds) has been proven to minimise bleeding events and complications (Manco-Johnson et al., 2007). Since the 1990s, recombinant FVIII concentrates have been standard-of-care treatment options for patients with congenital HA (Kingdon and Lundblad, 2002). Treatment regimens to achieve optimal prevention of bleeding events vary individually; some patients tolerate nadir FVIII levels of 1%,

whereas others require higher nadir FVIII levels to achieve the desired therapeutic outcome (Ahnström et al., 2004; Collins et al., 2010). Current standard prophylactic regimens commonly use infusion therapy administered 3 times weekly; other regimens require every other day administration, depending on the patient's needs (Shapiro, 2013). Furthermore, the risk of bleeding is not directly proportional to the severity of the disease as measured by the percentage of the normal FVIII plasma procoagulant levels. Thus, a subset of patients with non-severe disease severity have a severe bleeding phenotype that require prophylactic treatment (den Uijl et al., 2014).

The development of inhibitory alloantibodies (inhibitors) occurs in approximately 20%–30% of patients with severe congenital HA and in 3%–13% of those with moderate or mild disease (Franchini and Mannucci, 2013). The only haemostatic options previously available were pro-thrombotic coagulation factors that augment other parts of the coagulation cascade (i.e., "bypassing agents") (Srivastava et al., 2020).

Hemlibra (also known as emicizumab, ACE910, and RO5534262) is a recombinant, humanised, bispecific, immunoglobulin G4 monoclonal antibody (IgG4) that binds with moderate affinity to activated factor IX (FIXa) and factor X (FX). In patients with congenital HA, Hemlibra bridges FIXa and FX to restore the function of missing activated FVIII that is needed for effective haemostasis. In patients with congenital HA, haemostasis can be restored irrespective of the presence of FVIII inhibitors, as Hemlibra shares no sequence homology with FVIII. In addition, Hemlibra offers the subcutaneous (SC) administration, removing the need for venous access. The recommended dose for emicizumab is 3 mg/kg of bodyweight weekly during the first 4 weeks. Maintenance dosage from week 5 and onwards is either 1.5 mg/kg weekly, 3 mg/kg every 2 weeks, or 6 mg/kg of bodyweight every 4 weeks. Because of the possibility of markedly extended dosing intervals, to once weekly or even less frequently, this compound dramatically change the treatment of patients with congenital HA with and without FVIII inhibitors who need effective, safe, and convenient prophylactic therapy.

Hemlibra received a marketing authorisation (MA) valid throughout the EU on 23 February of 2018 for the indication: routine prophylaxis of bleeding episodes in patients with congenital HA with FVIII inhibitors. On 31 January of 2019, the EU committee for medicinal products for human use (CHMP) adopted a favourable opinion on the expansion of the indication of Hemlibra to patients with severe congenital HA without FVIII inhibitors. Hemlibra can be used in all age groups.

6.2. RATIONALE

The marketing authorisation holder (MAH) submitted extension of indication for Hemlibra to include routine prophylaxis of bleeding episodes in patients with congenital HA without FVIII inhibitors who have moderate disease ($1\% \le FVIII \le 5\%$) with severe bleeding phenotype.

Hemlibra—F. Hoffmann-La Roche Ltd Protocol BO44691, Version 2.0

On 15 December 2022, the CHMP issued a positive opinion for this new extension of indication; the European Commission (EC) decision was received on 23 January 2023.

To fulfil the category 3 post-authorisation safety study (PASS) regulatory commitment in the EU, the MAH proposed a multi-registry, non-interventional (NI) PASS to characterise the important potential risk of thromboembolic (TE) events (not associated with aPCC exposure) specifically and inform on the long-term safety profile of emicizumab in the new patient population.

7. RESEARCH QUESTION AND OBJECTIVES

7.1. RESEARCH QUESTION

The aim of the study is to evaluate the long-term safety profile of emicizumab in patients with moderate congenital HA ($1\% \le FVIII \le 5\%$) without FVIII inhibitors and with severe bleeding phenotype and who are exposed to emicizumab in real-world settings, with a specific focus on TE events.

7.2. OBJECTIVES

The primary objective for this study is to determine the incidence of TE events.

The secondary objectives for this study are:

- 1. To determine the incidence of serious adverse events (SAEs).
- 2. To determine the incidence of thrombotic microangiopathy (TMA) events.
- 3. To determine the incidence of serious systemic hypersensitivity reactions, including anaphylaxis.
- 4. To characterise the risk profile in terms of pre-defined risk factors of TE events in the patient population.
- 5. To describe characteristics of TE events, SAEs, TMA events, and serious systemic hypersensitivity reactions, including anaphylaxis (e.g., diagnosis and symptoms).
- 6. To characterise the impact of the prior use of FVIII prophylaxis on the incidence of TE events, SAEs, TMA events, and serious systemic hypersensitivity reactions, including anaphylaxis.

8. RESEARCH METHODS

8.1. STUDY DESIGN

This is a NI, multi-country, registry-based PASS, longitudinal cohort study based on secondary use of data collected for patients of all ages with moderate congenital HA, without FVIII inhibitors and with severe bleeding phenotype, treated with emicizumab,

The data sources will include registries containing haemophilia patients, primarily based in the European region, but also data sources in the US, Canada and Australia are considered. Data collection will focus on secondary data routinely collected within the registries prior to and after patients initiate treatment with emicizumab. The data sources under consideration are listed in section 8.4. The data will be extracted from the registries annually and pooled to a common data model (CDM) to perform pooled analyses. The planned first data extraction is approximately 1 year after registration of the protocol in the EU PAS register, the study launch. The last data extraction will the date after the last included patient has completed their minimum follow-up of 4 years, Q4 2030. Based on this, the final study report will be submitted as a standalone document in the EU PAS registry. Interim reports will be included in the PSUR/PBRER.

The aim of the study is to include approximately 200 patients who will be followed for a minimum of 4 years from the initiation of emicizumab treatment. According to previous clinical data, this follow-up time will be adequate to observe potential adverse events (AEs) and specifically TE events in the enrolled population (see section 8.6. for details). The overall study duration is expected to last a minimum of 6 years considering a 2-year period from approval of protocol until the end of patient inclusion. However, the overall length of study period will be dependent on MA of emicizumab for moderate patients without FVIII inhibitors. The study length may be adapted to each participating country, and, if needed, the study period may be amended to achieve the targeted sample size (see section 8.5. for details).

Data extracted from the registries will include data that pertains to haemophilia diagnosis, haemophilia disease and treatment history, emicizumab treatment, patient's demographic characteristics, ongoing and previous medication use (whether related to haemophilia or not), and a list of TE risk factors (see section 8.3. for details).

For an overview of the study design and assessment periods see Figure 1.

Hemlibra—F. Hoffmann-La Roche Ltd Protocol BO44691, Version 2.0

Figure 1. Overview of study design and assessment periods.

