8.5.2. Minimum required sample size

To assess whether the real-world estimate obtained in section 8.5.1. will be adequate to investigate the primary study objective of determining the crude IR of 1st TE, a statistical estimation is presented below. A target sample size of ~200 exposed patients with an average follow-up of 4 years for each patient was considered. From simulation runs, this target sample size will ensure 88% probability that the 95% Clopper-Pearson confidence

interval (CI) of the crude IR does not exceed a threshold value of one event per 100 person-years (PY), considering the expected IR of AEs for the primary objective of 0.15 events per 100 PY.

In the emicizumab clinical trial program, a 0.38% incidence risk (3 out of 798 patients) was observed and an IR of 0.15 events per 100 PY with a 95% CI (0.03-0.44) for serious TE events not associated with concomitant aPCC in HA patients. The average duration of exposure was 138 weeks (2.65 years), with a median duration of exposure of 104 weeks (2 years). These findings align with the TE event risk observed in the European Haemophilia Safety Surveillance (EUHASS) registry, which was 0.40% (4 out of 1319 patients).

Table 9 presents alternative scenarios for the estimation's accuracy, defined as the probability that the upper limit of the IR 95% CI does not exceed a certain threshold. This is obtained via calculations with different target sample sizes. For the first alternative scenario, the same expected event rate as above is assumed, and the threshold value for the 95% CI remains as indicated previously. In the second scenario the expected event rate is increased to 0.5 per 100 PY and the threshold value for the 95% CI is changed to 1.5 events per 100 PY.

	Accuracy CI								
Target Sample Size	Expected event rate: 0.15 per 100 PY Threshold: 1 event per 100 PY	Expected event rate: 0.5 per 100 PY Threshold: 1.5 event per 100 PY							
N=175	72%	73%							
N=200	88%	79%							
N=225	95%	83%							

Table 9. Accuracy estimation for different targets of sample sizes, expected event rates and Clopper-Pearson 95% CI threshold values.

CI, Confidence Interval; N, Sample Size; PY, Person Years.

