8.7.2. Planned Analyses

For the analysis of the primary objective and secondary objectives 1, 2, and 3 the overall crude and crude stratified IRs will be calculated. The person-time of each patient will be based on the follow-up and censoring criteria presented in section 8.2.4. and 8.2.5.

For the calculation of crude IRs, the denominator will be the pooled person-time of all the patients within the cohort. The patient time-at-risk will be calculated from index date until the date of an incident event or censoring, whichever occurs first. All first events occurring during follow-up period will be counted in the total number of events. Crude IRs will be presented per 100 PY with 95% CI.

For the primary objective, the numerator will be the number of first TE events of all patients within the cohort. For secondary objectives 1, 2, 3 the numerator will be the number of first occurrences of any SAE; TMA events or serious systemic hypersensitivity reactions, including anaphylaxis; respectively.

For the analysis of secondary objective 4, calculation of crude stratified IRs of 1st TE events will be done. The events will be counted for each category/stratum of relevant pre-defined risk factors (see section 8.3.2.4. for a listing of considered risk factors). More details on the risk factor based tabulations will be presented in SAP.

For analysis of secondary objective 5, characteristics of TE events, SAEs, TMA, and serious systemic hypersensitivity reactions, including anaphylaxis (e.g., diagnosis and symptoms), will be tabulated. In addition, time to 1st TE event; time to 1st TMA event; time to 1st serious systemic hypersensitivity reactions, including anaphylaxis; and time to any 1st SAE event will be described by Kaplan-Meier curves.

For analysis of secondary objective 6, calculation of crude IR and crude incidence proportion of TE, TMA events, SAEs and serious systemic hypersensitivity reactions, **Hemlibra—F. Hoffmann-La Roche Ltd** Protocol BO44691, Version 2.0

including anaphylaxis, will be calculated and tabulated for FVIII prophylaxis use (yes/no) prior to emicizumab treatment.

Patient demographic and clinical characteristics will also be tabulated in relation to the AEs (TE events, SAEs, TMA events and serious systemic hypersensitivity reactions, including anaphylaxis) and in total.

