8.9.2. Information Bias

Information bias is the bias arising from the systematic measurement error or misclassification of patients. As this is a registry-based study the validity of the findings of the study will solely rely on the validity, quality and completeness of the information recorded in the registries. There is potential for heterogeneity in the type of data collected from the registries regarding emicizumab treatment exposure, e.g., the exact dates of dispenses and SC injections, that could potentially result in exposure misclassification that are registry specific. Depending on the registry, specific limitations for exposure classification could be developed to avoid misclassification. There is also potential for heterogeneity in the study population because of different lookback periods when patients enrol in different registries. In certain cases, the lookback period might not be fully 12 months and the inclusion criteria regarding previous HA outcomes and HA treatments approximately 12 months prior to the index date (see section 8.2.6.1.) may not be fully confirmed if emicizumab treatment initiation (index date) coincides with patient enrolment into the registry.

In the primary incidence analysis, we do not exclude patients with a history of TE events before the index date. Thus, there exists a possibility that individuals with prior TE **Hemlibra—F. Hoffmann-La Roche Ltd**

Protocol BO44691, Version 2.0 events are included in the crude IR of TE. In the planned analysis of secondary objective 4 the IR would be tabulated based on the history of TE events during the lookback period. This would ensure that the incidence would be calculated for patients treated with emicizumab without any prior TE events during the lookback period and in addition contribute valuable evidence on the event rate among patients treated with emicizumab who have a history of TE events.

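### Section 8.1 calls the follow-up adequate to observe TE events, but the planning rate implies about 1.2 of them: the study can bound the overall TE rate, while stratified TE rates will be largely uninformative

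*Protocol*

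**What the plan says.** **Adequacy (8.1).** "The aim of the study is to include approximately 200 patients who will be followed for a minimum of 4 years". The protocol then appeals to previous clinical data and states that "this follow-up time will be adequate to observe potential adverse events (AEs) and specifically TE events in the enrolled population (see section 8.6. for details". Section 8.6 covers data management; study size is in 8.5.

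**Sizing (8.5.2).** "A target sample size of ~200 exposed patients with an average follow-up of 4 years for each patient was considered", "considering the expected IR of AEs for the primary objective of 0.15 events per 100 PY". The stated result is an 88% probability that the 95% Clopper-Pearson interval does not exceed 1 event per 100 person-years (PY). The rate comes from the emicizumab trial programme: 3 of 798 patients, 0.15 per 100 PY (95% CI 0.03 to 0.44), for serious TE events not associated with aPCC. On exposure in that programme: "The average duration of exposure was 138 weeks (2.65 years), with a median duration of exposure of 104 weeks (2 years".

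**Use of the TE events.** For objective 4, section 8.7.2 plans crude first-TE rates by risk factor: "The events will be counted for each category/stratum of relevant pre-defined risk factors". Section 8.3.2.4 lists 29 candidates. Objective 6 is worded "To characterise the impact of the prior use of FVIII prophylaxis on the incidence of TE events" and the other safety events. Section 8.9.2 says that tabulating by TE history will "contribute valuable evidence on the event rate among patients treated with emicizumab who have a history of TE events".

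**Safeguards.** Section 8.7.1 declares the study descriptive, without formal comparison. Sections 8.7.1 and 8.7.3 make stratification and subgroup priority depend on data availability and patient numbers; neither mentions event numbers. Section 8.9 does not list sparse TE events as a limitation, and the expected TE count appears nowhere.

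**The concern.** The adequacy sentence gives the design a property that the sizing section does not establish. Section 8.5.2 asks whether the upper confidence limit will stay low. That happens when few events occur, so it does not show that events will be seen. If the expected count is about one, most strata of the TE analyses will hold no event, and any event will fall in one stratum of each factor more or less by chance.

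This is a regulatory-commitment study of TE risk, so the wording matters. A reader of the protocol would expect it to show how TE incidence varies with risk factors and prior prophylaxis. A zero rate in a small stratum could be taken as reassurance, and the stratum with the single event as the group at risk.

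**Working it through.** **Inputs.** N = 200, 4 years on average, 0.15 per 100 PY, threshold 1 per 100 PY (8.5.2); rate CI 0.03 to 0.44 (8.5.2); alternative rate 0.5 per 100 PY (Table 9); projected uptake of 202, 324, 338 or 540 patients (Table 8); follow-up capped at 5 years (8.2.4).

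**Step 1: the plan's own figure.** Person-time is 200 × 4 = 800 PY. The Clopper-Pearson upper limit on 800 PY is 0.90 per 100 PY for 2 events and 1.09 for 3, so the criterion is met with at most 2 events. With events ~ Binomial(800, 0.0015), P(X ≤ 2) = 88.0%, against 88% stated. The same method gives 71.7% and 95.2% for N = 175 and 225 (stated 72% and 95%), and 72.6%, 78.6% and 83.2% in the second scenario (stated 73%, 79% and 83%). Table 9 is reproduced. The 88% is therefore the probability of seeing two events or fewer.

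**Step 2: expected TE events.** Mean = 800 × 0.0015 = 1.2. Under a Poisson model:
- P(0) = e^(−1.2) = 30.1%
- P(≤ 1) = e^(−1.2) × (1 + 1.2) = 66.3%
- P(≥ 2) = 33.7%

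**Step 3: range.**

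| Patients × years | Rate per 100 PY | Expected events | P(0) | P(≤ 1) |
|---|---|---|---|---|
| 200 × 4 | 0.15 | 1.2 | 30.1% | 66.3% |
| 202 × 4 | 0.15 | 1.21 | 29.8% | 65.8% |
| 200 × 5 | 0.15 | 1.5 | 22.3% | 55.8% |
| 324 × 4 | 0.15 | 1.94 | 14.3% | 42.1% |
| 338 × 4 | 0.15 | 2.03 | 13.2% | 39.8% |
| 540 × 4 | 0.15 | 3.24 | 3.9% | 16.6% |
| 200 × 4 | 0.03 | 0.24 | 78.7% | 97.5% |
| 200 × 4 | 0.44 | 3.52 | 3.0% | 13.4% |
| 200 × 4 | 0.5 | 4.0 | 1.8% | 9.2% |

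**Step 4: splitting the events.** The protocol gives no stratum sizes, so the shares below are assumptions. For a stratum with share s of the 800 PY and the same rate in both strata, the mean is 1.2s, and the exact upper 95% limit with no event is 3.689/(800s).

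| Share s | PY | P(no event in stratum) | P(event in both strata) | Upper limit if none, per 100 PY |
|---|---|---|---|---|
| 50% | 400 | 55% | 20% | 0.92 |
| 30% | 240 | 70% | 17% | 1.54 |
| 20% | 160 | 79% | 13% | 2.31 |
| 10% | 80 | 89% | 7.5% | 4.61 |
| 5% | 40 | 94% | 4% | 9.2 |

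Even with an equal split, as might arise for prior prophylaxis, both strata hold an event only one time in five. In a 10% stratum, no event leaves an upper limit of more than four times the planning threshold.

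**The case against.** The strongest replies, and what stands of each:

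- **The sentence in 8.1 is about duration.** Partly right. Four years exceeds the mean (2.65 years) and median (2 years) exposure of the programme that recorded the three events, so a reader should not infer from the 2-year median that 4 years is too short. The shortfall is in person-time: 798 × 2.65 ≈ 2,115 PY yielded three events, and 800 PY is about 38% of that. The sentence still claims adequacy for TE events in the enrolled population, and that depends on the number of patients.
- **The study is descriptive and its rates carry 95% CIs.** This stands. A zero would be shown with its wide interval, and misreading is a risk rather than a certainty. But objective 6 speaks of impact and 8.9.2 of valuable evidence, and both go beyond description.
- **Objective 4 needs no events.** Largely right. It concerns the risk profile of the patient population, which baseline prevalence describes even if no TE event occurs. A reader might infer that objectives 4 and 6 cannot be answered at all. The documents do not support that; only the stratified TE rates are uninformative.
- **Counts may be higher.** True. The cohort could reach 540, follow-up can run to 5 years, and the 0.15 rate covers serious non-aPCC events while the endpoint is all recorded TE events. Censoring at discontinuation works the other way. No single variation tabulated above gives more than 4 expected events, few to spread over 29 factors.
- **Details belong in the SAP.** Accepted for the numerical event minimum. The adequacy claim, the objectives and the 8.9.2 statement are fixed in the protocol.

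**Conclusion.** The point holds in limited form. The adequacy claim in 8.1 has no support where it points and does not follow from 8.5.2. On the planning assumptions the study expects 1.2 first TE events, with a 30% chance of none and 66% of at most one. The chance of none ranges from 4% (540 patients) to 30% at the planning rate, and from 79% to 3% across the rate's CI at 800 PY. Stratified TE rates for objectives 4 and 6 will be computable but largely uninformative.

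A reader might also infer that the study is too small for its primary objective. It is not: the 88% is reproduced, and bounding the overall TE rate is what the design can do. The SAE part of objective 6 is untouched by this calculation, and no planned analysis becomes invalid.

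The conclusion assumes Poisson events at a constant rate and the person-time of 8.5.2. The stratum results also rest on the assumed shares.

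**What to change.** - **8.1:** replace the adequacy claim with the expected TE count and the probability of none, say that the study bounds the TE rate, and point to 8.5 instead of 8.6.
- **8.9:** list TE sparsity as a limitation, and drop the claim in 8.9.2 about evidence on the event rate in patients with a TE history.
- **Objective 4 (8.7.2):** make baseline prevalence of each risk factor the main output. Describe TE cases by risk factor in the form each registry's data permit allows, aggregated where patient-level data are not available. A uniform case-by-case listing is not feasible: Table 7 shows no patient-level access for WBDR and CBDR, which hold 2987 + 299 = 3286 of 5307 moderate patients (62%).
- **8.7.2 and 8.7.3:** give stratified TE rates only once a pooled event count, pre-specified in the SAP, is reached, rather than by patient numbers alone.
- **Objective 6:** for TE, describe incidence by prior prophylaxis instead of characterising its impact.

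The cost is protocol and SAP wording. The claims become more modest and fewer stratified TE rates are reported. Sample size, data sources and the primary analysis are unchanged.
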